### 5.8.2 Analyses including different follow-up time points

The analyses specified for the primary and secondary endpoints in Sections 5.2 and 5.3 at 24 months of follow-up may be replicated at 3, 6 and 12 months of follow-up (i.e. analogous regression models will be used, but using endpoint data from 3, 6 and 12 months of follow-up instead of 24 months).

We may also jointly analyze all time points in a linear mixed model (to adjust for within-patient correlations). Patients will be treated as a random effects, and time points, randomization arm, age at baseline, sex and degree of tendon retraction will be included as fixed effects. Mixed effect models corresponding to analogous fixed effect model for individual time points will be used (i.e. a logistic mixed effect model where a logistic model was used for an individual time point, etc.). The mixed-effects model handles data missing at random, however drop-out processes can be missing not at random (MNAR). Therefore, we may use MICE also in the context of linear mixed model analyses. The MICE procedure will then be done analogously to what is described in Section 5.7.

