## 5.7 Missing data

All reasonable efforts will be taken to ensure that the level of missing data and loss to follow-up will be minimal.

Missing data can occur in different ways in the study: (1) individual questions in the instruments (e.g. the PHAT questionnaire) can be left unanswered; (2) data on specific endpoints may be entirely missing at different follow-up timepoints (due to a e.g. a functional test not being performed or data on a specific instrument not collected); and (3) patients can miss specific follow-up visits or drop out of the study altogether (resulting in no information on endpoint data for the corresponding follow-up timepoint or missing data on all subsequent follow-up timepoints).

Missing data on individual instrument (e.g. PHAT) questions will be imputed using predictive mean matching (PMM), with donor pool (k)=5.

Missed follow-up visit at specific follow-up timepoints will be handled using a multiple imputation by chained equations (MICE). The multiple imputation protocol will be based on models for predicting outcomes at specific follow-up timepoints based on outcomes data recorded at other time points together with treatment group, patient age, sex and degree of tendon retraction. For example, a missing PHAT score at 24 months will be imputed based on a regression model fit to

data from timepoints 3, 6, and 12 together with treatment group, patient age, sex and degree of tendon retraction.

We will generate 1,000 datasets with imputed outcome data, which will be analyzed separately. We will then use Rubin's rules to pool the estimated absolute differences in PHAT score and standard errors.

The global COVID pandemic has occurred during the conduct of this trial. COVID and restrictions have had a major impact on the healthcare situation and has resulted in rescheduled and cancelled follow-up visits in PHACT. Therefore, visits will be analyzed as follows:

- Visits occurring 2.5 to 4.5 months after randomization (or baseline for the observational cohort) will be considered as the 3 month visit.
- Visits occurring 4.5 to 9 months after randomization (or baseline for the observational cohort) will be considered as the 6 month visit.
- Visits occurring 9 to 18 months after randomization (or baseline for the observational cohort) will be considered as the 12 month visit.

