#### 5.8.5 Sensitivity analysis of the primary endpoint

The PHAT score is constrained between 0 and 100. For the primary analysis, we use linear regression, which is not constrained to values between 0 and 100. As a sensitivity analysis, we may use beta regression instead of linear regression to analyze the primary endpoint (using the same covariates), since beta regression is bounded to an interval between 0 and 1. Using the fitted beta regression model, we can compute the difference in PHAT score using regression standardization to marginalize across the covariate distributions.

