## 7.3 Changes to the SAP as a result of the review process

As part of the review process, two main changes were made to the analysis of the trial. Specifically:

1. Instead of using the ITT population for the primary analysis, the PP population was used.
2. Instead of performing analyses where the RCT cohort and the observational cohort were analyzed together, separate analyses were conducted and reported for two cohorts.

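### Section 5.8.2 offers MICE as the answer to MNAR drop-out, but the Section 5.7 MICE assumes MAR, and nothing in the SAP relaxes that for the 24-month PHAT contrast

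*SAP*

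**What the plan says.** SAP Section 5.8.2 describes an optional repeated-measures analysis: "We may also jointly analyze all time points in a linear mixed model". It credits that model with validity under MAR, then says "drop-out processes can be missing not at random (MNAR). Therefore, we may use MICE also in the context of linear mixed model analyses". The imputation is not a new one: "The MICE procedure will then be done analogously to what is described in Section 5.7".

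Section 5.7 builds the imputation on "models for predicting outcomes at specific follow-up timepoints based on outcomes data recorded at other time points together with treatment group", plus age, sex and degree of tendon retraction. Its worked example predicts a missing 24-month PHAT from the 3-, 6- and 12-month values and those covariates. It plans 1,000 imputed datasets, pooled by Rubin's rules. For missed visits the wording is not optional: they will be handled this way.

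The primary contrast is PHAT at 24 months, with a margin of 10 points tested at one-sided 0.05 and then 0.025 (Section 5.2). Section 7.3 later changed the primary population: "Instead of using the ITT population for the primary analysis, the PP population was used". It did not change the handling of missing data.

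**The concern.** The SAP names a threat (drop-out that depends on the unseen outcome) and offers a remedy with the same weakness as the method it is meant to repair. A reader of Section 5.8.2 would believe MNAR had been dealt with.

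The gap reaches the main result because the same imputation fills in missed 24-month visits. PHAT is self-reported (Section 4.2.1), and only the testing physiotherapists and the statisticians are blinded (Section 4.3), so drop-out that differs by arm is plausible. Take a higher PHAT as better, which the SAP does not spell out. If non-operative patients who leave do worse than their earlier scores predict, and operative patients who leave do not, imputation under MAR moves the estimate towards non-inferiority. No planned analysis would reveal it.

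**Working it through.** **1. Does the Section 5.7 imputation go beyond MAR?** Its predictors are observed outcomes at other visits, arm, age, sex and retraction. The mixed model in Section 5.8.2 is listed as follows: "time points, randomization arm, age at baseline, sex and degree of tendon retraction will be included as fixed effects", with patients as random effects. Neither contains a shift, a pattern indicator, a reference-based rule or a selection model. Imputed values therefore follow the conditional distribution seen in patients who stayed, which is MAR. Section 5.7 does not use the term; the assumption follows from the model it describes.

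**2. Does any other section relax MAR for 24-month PHAT?**
- Section 5.1: the weights model protocol adherence, not missing outcomes.
- Section 5.8.4 (cross-overs): definition of a cross-over only.
- Section 5.8.4 (observational cohort): the weights model treatment choice.
- Section 5.8.5: beta regression, because "The PHAT score is constrained between 0 and 100".
- Section 5.8.6: site adjustment.
- Section 7: relative risks, limb symmetry, change of population and separate cohort analyses.

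None does.

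**3. Reproducing the plan's figure.** Section 6.2, Table 1: 60 per arm, 20% dropout, SD 20, margin 10, one-sided 0.05, power 79%. With 48 per arm, SE = 20 × √(2/48) = 4.08, and power = Φ(10/4.08 − 1.645) = 78.9%. This agrees, so the same SE is used below.

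**4. Type I error if MAR fails in one arm.** Inputs from the SAP: 60 per arm, SD 20, margin 10, both alpha levels. The 10% and 20% missing fractions are Table 1's dropout levels; 1/6 is the planned allowance from 60 to 50. Assumptions: a 5% missing fraction, and a shortfall of 10 points beyond the MAR prediction, in non-operative drop-outs only. The analysis is unweighted.

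Bias = f × (non-operative shortfall − operative shortfall); SE = SD × √(2/[n(1 − f)]); type I error = 1 − Φ(z − bias/SE), with z = 1.645 or 1.960.

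| Missing f | Bias | SE | Type I at 0.05 | Type I at 0.025 |
|---|---|---|---|---|
| 5% | 0.50 | 3.75 | 6.5% | 3.4% |
| 10% | 1.00 | 3.85 | 8.3% | 4.5% |
| 1/6 | 1.67 | 4.00 | 11.0% | 6.1% |
| 20% | 2.00 | 4.08 | 12.4% | 7.1% |

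Equal shortfalls give bias 0 and leave 5% / 2.5%. A 10-point shortfall in operative drop-outs only, at 1/6 missing, gives 2.0% / 0.9%, which is conservative.

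**5. Tipping point at an estimated difference of 0.** Tipping shortfall = (10 − z × SE)/f, ignoring the small change in SE.
- 10% missing: (10 − 1.645 × 3.85)/0.10 ≈ 37 points; at z = 1.960, about 25.
- 20% missing: (10 − 1.645 × 4.08)/0.20 ≈ 16 points; at z = 1.960, about 10.
- With SD 16, 20% missing (SE 3.27): about 23 and 18 points.

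**6. How large a shortfall might survive imputation?** A large-sample simulation took 20% missing in one arm, depending on 24-month PHAT, with SD 20, an assumed within-patient correlation of 0.4 to 0.8 and an assumed log-odds slope of 0.5 or 1 per SD. Complete-case bias was 1.9 to 3.5 points. Imputing from the 3-, 6- and 12-month values left 0.5 to 2.6 points. Dividing by 0.20 gives shortfalls of about 2.5 to 13 points, so 10 lies in the upper part of that range. The imputation reduces MNAR bias but does not remove it.

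**The case against.** The wrong statement sits in an analysis that is optional twice over, and no planned result depends on that sentence. Section 5.7 itself says nothing false. This stands: what reaches the primary contrast is an untested assumption, not a false statement. It is still fair to raise, because the SAP itself names MNAR drop-out as a threat.

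Section 5.7 also gives context that softens the point. The one study-specific cause of lost visits it names is COVID and its restrictions, which may be unrelated to PHAT. It also counts any visit after 18 months as the 24-month visit, which lowers the missing fraction. With 5% missing and an estimate of 0, the tipping points are about 77/53 points, since (10 − 1.645 × 3.75)/0.05 ≈ 77, so the result would hardly be in doubt. This stands as well, though Section 5.7 also allows for drop-out in general.

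Two stronger readings are tempting and not supported. A reader might infer that the imputation adds nothing to the mixed model. That is too firm: Section 5.7's general rule can take in baseline PHAT, which is not among the listed fixed effects, so MAR may become somewhat more plausible. It remains MAR. A reader might also compute tipping points near 0 at an estimate of −2 (SD 20, 20% missing, one-sided 0.025) and call the result fragile to missing data. There, 10 − 2 = 8.0 already equals 1.96 × 4.08, so the MAR analysis is itself on the margin. That reflects precision and the estimate, not missingness.

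**Conclusion.** The stated remedy does not address the stated threat: both the mixed model and the Section 5.7 MICE assume MAR. The 24-month PHAT contrast depends on that assumption, and no section examines a departure from it. This is certain from the text.

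The consequence is not. A reader might infer that non-inferiority would be wrongly declared, or that 12.4% is the trial's error rate. The documents support neither. They give no missing fraction and no information on how drop-outs fared, and the bias could be nil or run against the claim. The error rates in the working assume a one-sided shortfall in every non-operative drop-out, SD 20 and the unweighted 60-per-arm design. The weighted PP population is smaller by an amount that the SAP does not state. The point should be corrected; it does not show the conclusion to be wrong.

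**What to change.** In Section 5.8.2, delete the inference from MNAR to MICE and state that both the mixed model and the Section 5.7 MICE assume MAR.

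Add a delta-adjusted (pattern-mixture) version of the Section 5.7 imputation for 24-month PHAT:
- Shift the imputed values, for example in steps of 5 points, separately in each arm, and keep them within 0 to 100. Report the mean shift actually applied.
- Extend the grid until the 10-point margin is no longer excluded or the bound of the scale is reached. At 10% missing, a grid that stops at 20 points would miss the tipping point.
- Report the tipping point at one-sided 0.05 and 0.025, with the number of imputed values per arm, in the PP population (with its adherence weights) and in the ITT population.

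Section 7 reports analyses already done, so this can only be post hoc. Label it so in a dated addendum, as Section 3 requires. It needs no new data: a shift applied to the 1,000 imputed datasets already planned, and one extra table. The downside is that the result may look less favourable.

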#### 5.8.4 Sensitivity analysis with respect to definition of cross-overs

As specified in Section 5.1, non-operative treated patients who are treated operatively due to late complaints (>3 months after inclusion) will in PP and AS analyses be handled in two ways: (i) *not* considered crossovers, in which case we regard these sets of patients as a failed initial conservative treatment strategy, followed by surgery; (ii) considered as cross-overs (analogously to patients who switch groups early, i.e. within 3 months of randomization). We may perform sensitivity analyses using both these definitions of a cross-over from conservative to surgical treatment.

#### 5.8.4 Analyses including the observational cohort

The randomized and observational cohorts will be analyzed together propensity scores. The propensity score will be based on a logistic regression model including age, sex, study site, baseline IPAQ and the degree of tendon retraction as covariates. The propensity scores will be used to perform inverse probability of treatment weighting (IPTW) with stabilized weights. The propensity score is defined as  $e = P(A = 1|Z)$ , where A is treatment allocation (A=1 for surgical treatment and A=0 for conservative treatment) and Z are the covariates. The stabilized weights are then defined as  $W=A*Pr(A=1)/e+(1-A)*Pr(A=0)/(1-e)$ .

We may also perform analyses using the observational cohort that are analogous to the ones we will perform to contrast the two randomized arms, but instead contrasting the observational cohort with the randomized cohort or one of the randomized arms.

#### 5.8.5 Sensitivity analysis of the primary endpoint

The PHAT score is constrained between 0 and 100. For the primary analysis, we use linear regression, which is not constrained to values between 0 and 100. As a sensitivity analysis, we may use beta regression instead of linear regression to analyze the primary endpoint (using the same covariates), since beta regression is bounded to an interval between 0 and 1. Using the fitted beta regression model, we can compute the difference in PHAT score using regression standardization to marginalize across the covariate distributions.

#### 5.8.6 Sensitivity analysis of adjustment for site

Site is a stratification variable in the randomization. As such, it is advisable to adjust for site in the analysis of the primary and secondary endpoints. However, it is not unlikely that some sites will recruit a small number of patients. Adjusting for many small sites raises analytical problems for which there is no best solution. Analyses either ignoring site or adjusting for a large number of small sites might lead to confidence intervals that may be either too large or too small. Further, pooling small sites has no scientific justification. We will approach this problem as described below:

- If all sites have  $\geq 10$  patients included in the randomized cohort, we will adjust for site in the analyses. We may then conduct sensitivity analyses where site is not adjusted for to assess its impact on the results.
- If at least one site has  $< 10$  patients included in the randomized cohort, we will not adjust for site in the analyses. We may then conduct sensitivity analyses where site is adjusted for to assess its impact on the results.

# 6 Sample size

## 6.1 Original sample size calculations

In PHACT, the PHAT-score is used as the primary outcome measure. It has been previously shown that minimal detectable difference in PHAT is 16 points and SD about 15 to 20. The sample-size calculations assumed a noninferiority margin of 16, a one-sided alpha of 2.5, 80% statistical power, and a standard deviation of the PHAT score of 20, which yielded a required sample size per group of 25 patients. Assuming 20% drop-out rate, we aimed at a group size of 30 (total 60). As cross-over was expected, we also decided to continue recruitment until 30 patients in each arm had entered and initiated the allocated treatment.

## 6.2 Updated sample size calculations (181204)

The study progress and accrual are continuously monitored. Specifically, we have pre-specified an evaluation of the study after 60 included participants with a possible increase in the size of the study as a result of the evaluation if it is motivated by a greater dropout than expected or new vital information obtained from discussions with patients and clinical staff. The study has in December 2018 been ongoing for 14 months and about 50 patients have been included in the study. It is clear that our original estimate of the incidence of the injury was too low. We also conclude that the logistics and operational aspects of the study are well-functioning. Thus, we have the possibility to consider an increase in the size of the study. The study has a unique opportunity to answer not only the primary question but also to analyze the effect of age and the severity of the injury on the effect of the two treatments.

To do this, we have discussed the ethical aspects of such a change:

Pros:

- A larger number of patients in the study increases the power of the study; i.e. reduces the risk of type 2 errors.
- A larger number of patients provides a better basis for subgroup analyzes. This is something that in conversations with patients has emerged as a crucial aspect, as a specific patient is interested in the probable outcome for him or her (i.e. patients who have the same characteristics) rather than the overall result at the population level.

Cons:

If the study in its current form can deliver a clear result that affects the treatment of future patients, the dissemination of result will be delayed by the study becoming larger and a number of patients will be treated without the new knowledge being reported. We believe that this risk is limited and justified. Based on clinical experience and existing scientific literature, there are no indications that the treatment result differs clearly between the groups and a larger study size provides a greater opportunity for results that are conclusive and lead to a change in clinical practice.

In the light of the description and motivation above, we decided to make the following change to the trial: In the literature, surgical treatment is strongly advocated. We wish to analyze the study in such a way that we want to be sure that the non-surgical treatment is not worse than the surgical treatment with a certain margin (non-inferiority trial with respect to the PHAT score).

To achieve 85% power, with a one-sided alpha of 0.05, for demonstrating non-inferiority using a non-inferiority margin of 10, 50 patients in each arm are required (assuming a standard deviation of the PHAT score of 20; which in the scientific literature has been reported to be in the range of 16 to 21). Accounting for drop-out, we will include 60 participants in each trial arm in the randomized part of the trial. Table 1 gives estimated power for 60 patients in each trial arm (120 patients in total) under different assumptions and alpha levels.

N	Dropout (%)	SD	Alpha (one-sided)	Power (%)
120	0	20	0.05	85
120	0	20	0.025	77
120	10	20	0.05	82
120	10	20	0.025	74
120	20	20	0.05	79
120	20	20	0.025	69
120	0	16	0.05	95
120	0	16	0.025	92
120	10	16	0.05	93
120	10	16	0.025	90
120	20	16	0.05	92
120	20	16	0.025	86

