## 5.2 Primary endpoint

PHAT scores (measured at 3, 6, 12, and 24 months) will be assessed and contrasted between the two treatment groups using a linear regression model that adjusts for an indicator of randomized treatment group assignment and for factors used to stratify randomization (site), age, sex, and degree of tendon retraction. The primary analysis will contrast the randomized groups at 24 months in the ITT population (analyses using other follow-up time points are specified in Section 5.8).

Based on the existing literature the standard deviation of PHAT measurements is ~16 – 21. The non-inferiority margin was set to half of the standard deviation (=10). The non-inferiority margin was agreed upon at a consensus group meeting that included orthopedic surgeons and statisticians. The one-sided alpha level will be 0.05. If conservative treatment is non-inferior on the one-sided 0.05 alpha level, we will repeat the test using a one-sided alpha of 0.025.

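### SAP Section 6.2 says 50 patients per arm give 85% power; its own assumptions and Table 1 give about 80%, and 85% needs 58 to 59 per arm

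*SAP*

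**What the plan says.** Section 6.2 (updated sample size, December 2018) justifies the final size of the randomised cohort in two steps. The first gives the target, "To achieve 85% power, with a one-sided alpha of 0.05", and the number needed, "non-inferiority margin of 10, 50 patients in each arm are required (assuming a standard deviation of the PHAT score of 20". The second adds the allowance for losses: "Accounting for drop-out, we will include 60 participants in each trial arm in the randomized part of the trial". No dropout rate is attached to that step.

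Table 1 follows directly: "Table 1 gives estimated power for 60 patients in each trial arm (120 patients in total) under different assumptions and alpha levels". At SD 20 and one-sided alpha 0.05 it lists 85%, 82% and 79% power for dropout of 0%, 10% and 20%.

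Section 5.2 uses the same alpha for the primary analysis ("The one-sided alpha level will be 0.05"), with a repeat at 0.025 if the first test succeeds, so the two sections do not differ on that input.

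**The concern.** The sentence ties 85% power to 50 patients per arm before dropout. Table 1 ties the same 85% to 60 per arm with no dropout, at the same SD and alpha. If the sentence and the table rest on the same true difference, they cannot both be right.

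The sentence is the formal justification of the sample size. It tells the reader that 60 enrolled per arm secures 85% power with losses already covered. If 50 is wrong, nearly all of the step from 50 to 60 is needed just to reach 85%, and little is left for dropout. Section 7.3 also moves the primary analysis to the per-protocol population, which can only reduce the number analysed; the SAP does not say by how much.

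**Working it through.** **Inputs**

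- Power 85%, one-sided alpha 0.05, margin 10, SD 20, equal arms: Section 6.2.
- True difference: not stated; 0 is assumed. Section 6.2 says there is no sign of a clear difference between the treatments, and Table 1 fits this value (step 4).
- Comparison: two means, unadjusted. Section 6.2 claims no gain from covariates.

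**1. Check that the formula is the SAP's own.** Per arm, n = 2 × (SD/margin)² × (z for alpha + z for power)². Applied to Section 6.1 (margin 16, SD 20, one-sided alpha 2.5%, 80% power): 2 × (20/16)² × (1.960 + 0.842)² = 24.5, rounded up to 25. This matches the 25 stated there.

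**2. Number needed under Section 6.2.**

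- For 85%: 2 × (20/10)² × (1.645 + 1.036)² = 57.5, so 58 per arm. The exact noncentral t calculation needs 59 (84.9% at 58, 85.4% at 59).
- For 80%: 2 × (20/10)² × (1.645 + 0.842)² = 49.5, so 50 per arm (51 by the t calculation).

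The stated 50 is thus the normal-approximation answer for 80% power.

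**3. Power at 50 per arm.** The standard error is 20 × √(2/50) = 4. Power = Φ(10/4 − 1.645) = Φ(0.855) = 80.4%; the t calculation gives 79.9%.

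**4. Comparison with Table 1 (SD 20, one-sided alpha 0.05).**

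| Dropout | Evaluable per arm | Table 1 | Normal | t |
|---|---|---|---|---|
| 0% | 60 | 85% | 86.3% | 85.9% |
| 10% | 54 | 82% | 83.0% | 82.6% |
| 20% | 48 | 79% | 78.9% | 78.4% |

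All 12 rows of the table reproduce within 1.6 points. The largest gap is at SD 16, 10% dropout, alpha 0.05: 93% stated against 94.6% (normal) or 94.3% (t).

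**5. The table on its own.** Power rises with n, and 50 lies between 48 and 54. By the SAP's own figures, power at 50 lies between 79% and 82%.

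**6. Room for dropout at 60 enrolled per arm.**

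- 85% needs 58 or 59 evaluable: 1 − 58/60 = 3.3%, 1 − 59/60 = 1.7%. That is 1 or 2 losses per arm.
- Going from 60 to 50 would be a loss of 10/60 = 16.7%.
- For scale, keeping 85% after 10% dropout would take 58/0.9 to 59/0.9, i.e. 65 to 66 enrolled per arm; after 20%, 58/0.8 to 59/0.8, i.e. 73 to 74.

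**7. What would make 50 correct for 85%.** Changing one input at a time:

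- an SD of about 18.6 (normal) or 18.5 (t), equivalent to covariates explaining 1 − (18.6/20)² ≈ 13% to 1 − (18.5/20)² ≈ 14% of the variance;
- a one-sided alpha of about 0.072;
- a true advantage for non-operative treatment of about 0.7 points (2.681 × 4 = 10.7, against a margin of 10).

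Section 6.2 states none of these.

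**The case against.** The strongest reply is that little turns on the sentence. Table 1 stands right below it and gives a careful reader the correct order of power at 60 enrolled, with and without dropout. The text records a decision dated December 2018, and the current SAP is version 1.6 of April 2024, so no correction can alter recruitment. This stands, and it limits the harm to the headline claim.

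A second reply is that the real analysis may do better than the simple formula. Section 5.2 adjusts for age, sex and tendon retraction, Section 5.7 imputes missed visits from other time points, and the SD may be below 20. At 18.5, the midpoint of the reported 16 to 21, 50 per arm would give 85.5% (normal) or 85.1% (t). These points bear on the trial's actual power, which is not known here, but they do not rescue the sentence: it assumes SD 20, and neither it nor Table 1 invokes adjustment or imputation. The SD argument also cuts both ways, since at 21 the power with 50 per arm is about 76% to 77%.

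A third reply is that a type II error of 20% belongs only to the case of exactly 50 evaluable per arm. That is right. Reading the step from 50 to 60 as an expected loss of 10 per arm is an inference, because the update gives no dropout rate.

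**Conclusion.** The sentence is wrong as written, and the table beside it contradicts it. Under the stated margin, SD and alpha, 50 evaluable patients per arm give about 80% power rather than 85%, so the type II error at that number is about 20% rather than 15%. The number needed for 85% is 58 to 59, which is 8 to 9 more per arm.

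The exact figures rest on a true difference of 0 and an unadjusted comparison of two equal arms. The contradiction with Table 1 needs only that the sentence and the table share the same true difference. The SAP does not show how the error arose; one possibility is that the number for an 80% target was paired with the 85% from the row for 60 per arm.

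The error affects the stated justification only and should be corrected. Table 1 is sound to within 1.6 points.

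**What to change.** Correct the sentence in Section 6.2 along these lines: *with one-sided alpha 0.05, margin 10, SD 20 and a true difference of 0, 50 evaluable patients per arm give about 80% power; 85% requires 58 to 59 evaluable per arm.* Then state the dropout rate behind the 60 per arm, or say that none was fixed, and refer to Table 1 for power at 60 enrolled (85%, 82% and 79% at 0%, 10% and 20% dropout). A short note that Table 1 can differ from the closed formula by up to 1.6 points would explain why it shows 85% at 60; the table itself can stay.

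Because the text records a 2018 decision, a dated correction entered in the revision history is a suitable form.

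The cost is one sentence in the SAP and in any report that repeats it. Margin, alpha, analysis and number of patients do not change. The headline power becomes less favourable.

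### Table 1 gives power for an ITT analysis with dropout only; Section 7.3 makes the weighted PP population primary and the power is not restated

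*SAP*

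**What the plan says.** - SAP 6.1 (original size) states that cross-over was expected. It answers this with a recruitment rule, to "continue recruitment until 30 patients in each arm had entered and initiated the allocated treatment".
- SAP 6.2 (December 2018) starts from "To achieve 85% power, with a one-sided alpha of 0.05" and says that "using a non-inferiority margin of 10, 50 patients in each arm are required", "assuming a standard deviation of the PHAT score of 20". It then says: "Accounting for drop-out, we will include 60 participants in each trial arm in the randomized part of the trial". Table 1 gives power for 120 patients at 0, 10 and 20% dropout, SD 20 or 16, and one-sided alpha 0.05 or 0.025. It has no cross-over column. Section 6.2 neither repeats nor withdraws the 6.1 rule.
- SAP 5.2 places the primary analysis in the ITT population. If non-inferiority is shown at 0.05, "we will repeat the test using a one-sided alpha of 0.025".
- SAP 5.1 limits the PP population to patients who received their randomised treatment per protocol, weights them by the inverse probability of adherence, and uses a robust standard error. In the main PP analysis, non-operative patients who have surgery more than 3 months after inclusion do not count as cross-overs.
- SAP 7.3 (version 1.6, April 2024) records: "Instead of using the ITT population for the primary analysis, the PP population was used". No power figure accompanies the change.

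**The concern.** The only power statement in the current SAP describes an analysis set that keeps every randomised patient who stays in follow-up. The current primary test uses a smaller, weighted set. The sponsor had seen in Section 6.1 that switching treatment reduces the number of patients who inform a treatment comparison. The updated size shows no allowance for it, and the later change of population made such an allowance relevant to the primary test.

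A reader who takes 79 to 85% (SD 20, alpha 0.05) or 69 to 77% (SD 20, alpha 0.025) as the power of the primary test is reading the wrong analysis. This matters most for the second step at 0.025, where power is lowest and an inconclusive result is most likely to need interpreting.

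**Working it through.** **Inputs.** From SAP 6.2: 60 per arm, margin 10, SD 20 or 16 (literature range 16 to 21), one-sided alpha 0.05, with 0.025 from SAP 5.2. True difference 0 is an assumption. The SAP states no value, but says "there are no indications that the treatment result differs clearly between the groups", and 0 reproduces Table 1. The cross-over proportion x is not in the SAP; 5, 10 and 20% are assumed, equal in both arms unless stated.

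**Formulas.** With dropout d, the evaluable number per arm is n = 60 × (1 − d) × (1 − x). The noncentrality is λ = 10 / (SD × √(2/n)). Power is the probability that a noncentral t with 2n − 2 degrees of freedom and noncentrality λ exceeds its one-sided critical value. The normal approximation is Φ(λ − z), with z = 1.645 or 1.960.

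**Step 1: the plan's own table (x = 0), SD 20.**

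| Dropout | n per arm | Table 1 (0.05 / 0.025) | Noncentral t | Normal |
|---|---|---|---|---|
| 0% | 60 | 85 / 77 | 85.9 / 77.5 | 86.3 / 78.2 |
| 10% | 54 | 82 / 74 | 82.6 / 73.1 | 83.0 / 73.8 |
| 20% | 48 | 79 / 69 | 78.4 / 67.9 | 78.9 / 68.8 |

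All 12 rows, including SD 16, agree within 1.3 points by noncentral t. Table 1 is sound for dropout alone.

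**Step 2: add PP exclusions (noncentral t, alpha 0.05 / 0.025).**

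| Dropout | x | n per arm | SD 20 | SD 16 |
|---|---|---|---|---|
| 10% | 0% | 54.0 | 82.6 / 73.1 | 94.3 / 89.6 |
| 10% | 5% | 51.3 | 80.8 / 70.8 | 93.3 / 88.0 |
| 10% | 10% | 48.6 | 78.9 / 68.4 | 92.1 / 86.2 |
| 10% | 20% | 43.2 | 74.5 / 63.2 | 89.2 / 81.9 |
| 20% | 0% | 48.0 | 78.4 / 67.9 | 91.8 / 85.8 |
| 20% | 5% | 45.6 | 76.6 / 65.6 | 90.6 / 83.9 |
| 20% | 10% | 43.2 | 74.5 / 63.2 | 89.2 / 81.9 |
| 20% | 20% | 38.4 | 70.1 / 58.0 | 85.7 / 77.1 |

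The cost should be read against the x = 0 row, not against the printed table, since up to about 1 point of the SD 20 differences is method. Like for like at SD 20, cross-over of 5, 10 and 20% costs about 2, 4 and 8 points at 0.05, and about 2, 5 and 10 points at 0.025.

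**Step 3: variations (normal approximation, SD 20, 10% dropout, alpha 0.05; 83.0% with no cross-over).**
- Loss in one arm only: 81.2% at 10% and 78.9% at 20%, against 79.4% and 75.1% when both arms lose patients. The cost is about half.
- Weighting: if the adherence weights carry an assumed design effect of 1.05, 1.1 or 1.2, the 79.4% at 10% cross-over becomes 77.7, 76.0 or 72.7%.

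**Step 4: the 50-per-arm sentence.** With n = 50, λ = 10 / (20 × √0.04) = 2.5, and Φ(2.5 − 1.645) = 80.4% (79.9% by noncentral t), not 85%. For 85%, n = 2 × (1.645 + 1.036)² × 20² / 10² = 57.5, so about 58 evaluable per arm. Table 1 agrees: it reaches 85% only at 60 per arm without dropout, and gives 79% at 48 and 82% at 54.

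**The case against.** The strongest reply is that Section 6.2 was coherent when written. In December 2018 the primary analysis was ITT, cross-overs stay in ITT, and dropout was the only loss of patients to allow for. That stands: the gap was opened by Section 7.3, and Table 1 contains no arithmetic slip.

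A reader might infer that Section 6.2 abandoned the protection in Section 6.1. The SAP does not say so. If the rule carried over, with 60 per arm starting the allocated treatment, Table 1 would apply to the PP set roughly as it stands. The silence is itself the thing to resolve.

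A reader might also infer that all cross-overs leave the primary analysis. Section 5.1 keeps late surgery in the main PP set, so only early switchers and other non-adherent patients are lost.

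Table 1 covers part of the range already. Dropout of 10% with cross-over of 10% is a 19% loss (1 − 0.9 × 0.9), which the 20% dropout row describes. Only larger combined losses fall outside the table. Covariate adjustment and imputation from earlier visits may recover some precision, and weighting may cost some; the SAP quantifies neither.

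Finally, power restated after the analysis changes no decision, and the confidence interval against the margin of 10 is what readers should use. This is right as far as it goes. But the SAP still presents a power table, and a reader needs to know which analysis it belongs to.

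**Conclusion.** The point holds as a gap in consistency between Sections 6.2 and 7.3. The stated power belongs to an ITT analysis with dropout only; for the PP analysis that is now primary it is too high by an amount that depends on exclusions the SAP does not quantify. At SD 20 and alpha 0.05 the loss is about 2 points at 5% cross-over, 4 at 10% and 8 at 20%, and about half that if only one arm loses patients. These figures assume a true difference of 0, no gain from adjustment or imputation and no loss from weighting, and that the 6.1 recruitment rule was not applied to the 60 per arm.

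It would go too far to conclude that the trial is underpowered or that the stated power was not delivered. No cross-over rate is given, and at SD 16 and alpha 0.05 power stays at about 85% or more in every combination tabulated above.

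One error in the same section does not depend on cross-over at all: 50 evaluable patients per arm give about 80% power, not 85%.

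**What to change.** Leave enrolment unchanged, and:
1. Label the existing Table 1 rows as ITT, dropout only.
2. State whether the Section 6.1 rule (recruit until the target number has started the allocated treatment) applied to the 60 per arm.
3. Add PP power for cross-over of 5, 10 and 20%, applied after dropout, at SD 20 and 16 and both alpha levels. Mark these rows as added after the change in Section 7.3, and state the assumed true difference and that weighting is not included.
4. Correct the sentence on 50 per arm: 50 evaluable per arm give about 80% power at one-sided 0.05, and 85% needs about 58.

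The cost is a few table rows and two or three sentences, with no extra patients. The downside is that the stated power becomes less favourable.
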